5.5 Adverse Event, Serious Adverse Event

The definitions of AE and SAE can be found in the Protocol Appendix 2. If an adverse event causality or severity is missing, the causality or severity will not be imputed.

The following imputation rules will be used for AE:

Imputation Rules for Partial Dates (D = day, M = month, Y = year)

Parameter	Missing	Additional Conditions	Imputation
Start date for AEs	D	M and Y same as M and Y of first dose of study treatment	Date of first dose of study treatment
		M and/or Y not same as date of first dose of study treatment drug	First day of month
	D and M	Y same as Y of first dose of study treatment	Date of first dose of study treatment
		Y prior to Y of first dose of study treatment but same as Y of screening date	Date of screening date
	D, M, Y	None – date completely missing	Date of first dose of study treatment
Stop date for AEs	D	M and Y same as M and Y of the Follow-up visit	Date of the Follow-up visit
		M and/or Y not same as date of the Follow-up visit	Use last day of month
	D and M	Y same as Y of the Follow-up visit	Date of the Follow-up visit
		Y not same as Y of the Follow-up visit	Use Dec 31
	D, M, Y	None – date completely missing	No imputation, but assume ongoing

Note: In all cases, if an estimated start date is after a complete stop date, use the first day of the stop date month. Similarly, if the estimated stop date is before a complete or imputed start date, use the last day of the start date month.

Statistical Analysis Plan Version Date: 19-Feb-2019

For example for AE start date imputation, if a participant is dosed on 15MAY2018 and has an AE start date reported as MAY2018 the imputation would be 15MAY2018, but if the AE start date was reported as JUN2018 the imputation would be 01JUN2018.

For example for AE stop date imputation, if a participant follow-up visit or cutoff date is 15MAY2018 and has an AE stop date reported as MAY2018 the imputation would be 15MAY2018, but if the AE stop date was reported as MAR2018 the imputation would be 31MAR2018.

5.6 Treatment-Emergent Adverse Event (TEAE)

Treatment-emergent adverse events (TEAEs) are those which first occur or increase in severity or relationship to study treatment after the first dose of study treatment and not more than 30 days after the last dose of study treatment. All Adverse Events (AEs) which change in severity or relationship to study treatment are assigned a new start date and captured as a new record.

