otherwise noted)		W 1	W 2	W 3	W 4	W 5	W 6		W 7	W 8	W 9	W 10	W 11	W 12	
Pharmacokinet	ic 🔼			San	npling	,									
Blood PK sampling	X	X	X		X	X	X	X	X	X			X	X	 See Section 8.6.3 and Table 12. *Day 4 and Day 46: Postinfusion: Sample may be collected ± 1 day at the PK visit. Day 15, Day 36, Day 50, and Day 57: Pre-infusion: Samples may be collected up to 120 minutes prior to the start of the infusion. Day 85: Collect sample 1 week after last administration. Day 8, Day 29, Day 43, and Day 78: Samples should be collected at: Pre-infusion: Samples may be collected up to 120 minutes prior to the start of the infusion. Mid-infusion: Samples should be collected ± 3 minutes within specified timeframe. If infusion is administered at a modified rate, the timing of collection of this sample should correspond to the middle of the modified infusion duration of the total administered dose. End-of-infusion: Samples should be collected 2 minutes within specified timeframe. This sample should be taken immediately prior to stopping the infusion. If the end of infusion is delayed to beyond the nominal infusion duration, the collection of this sample should also be delayed accordingly. Postinfusion: Samples should be collected 1 hour ± 3 minutes postinfusion.

Table 2 On-Treatment Procedural Outline IM025006: Part 1, Treatment Period (Day 4 through Day 85)

Procedure/Vi sit Day				12-	week,	, Doub	ole-Bl	ind, T	reatmo	ent Pe	eriod				Notes
(± 3 days for all visits unless	D 4ª	D 8	D 15	D 22	D 29	D 36	D 43	D 46 ^a	D 50	D 57	D 64	D 71	D 78	D 85	
otherwise noted)		W 1	W 2	W 3	W 4	W 5	W 6		W 7	W 8	W 9	W 10	W 11	W 12	

Table 2 On-Treatment Procedural Outline IM025006: Part 1, Treatment Period (Day 4 through Day 85)

Procedure/Vi sit Day				12-	-week,	, Doub	ole-Bl	ind, Tı	reatmo	ent Pe	eriod				Notes
(± 3 days for all visits unless	D 4ª	D 8	D 15	D 22	D 29	D 36	D 43	D 46 ^a	D 50	D 57	D 64	D 71	D 78	D 85	
otherwise noted)		W 1	W 2	W 3	W 4	W 5	W 6		W 7	W 8	W 9	W 10	W 11	W 12	

Table 2 On-Treatment Procedural Outline IM025006: Part 1, Treatment Period (Day 4 through Day 85)

Procedure/Vi sit Day	_			12-	-week	, Doub	ole-Bl	ind, T	reatm	ent Po	eriod				Notes
(± 3 days for all visits unless	D 4ª	D 8	D 15	D 22	D 29	D 36	D 43	D 46 ^a	D 50	D 57	D 64	D 71	D 78	D 85	
otherwise noted)		W 1	W 2	W 3	W 4	W 5	W 6		W 7	W 8	W 9	W 10	W 11	W 12	

On-Treatment Procedural Outline IM025006: Part 1, Treatment Period (Day 4 through Day 85) Table 2

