Procedure/Vi sit Day				12-	week,	Doub	le-Bli	ind, Tı	reatme	ent Pe	eriod				Notes
		D 8	D 15	D 22	D 29	D 36	D 43	D 46 ^a	D 50	D 57	D 64	D 71	D 78	D 85	
otherwise noted)		W 1	W 2	W 3	W 4	W 5	W 6		W 7	W 8	W 9	W 10	W 11	W 12	
Study Treatment	/Plac	ebo	Adm	inistra	ation (X = B	MS-9	86263	; O = 1	placel	bo)				
Study Treatment/ 45 mg BMS-986263 QW	Т	x X	Adm X	inistra X	ation (X = B	MS-9	86263	; O = 1	placel X	bo)	X	X		See Section 8.5.1 and Section 8.5.4.
45 mg BMS-986263		Т						86263				X X	X X		See Section 8.5.1 and Section 8.5.4. See Section 8.5.1 and Section 8.5.4.

O = placebo;

PK = pharmacokinetics;

SAE = serious adverse event; W = Week; WOCBP = women of childbearing potential

QW = every week;

^a Days 4 and 46: PK-only collection visits; see Table 12.

Table 3 On-Treatment Procedural Outline IM025006: Part 1, Follow-up Period (Day 99 through Day 253)

				24-w	eek, Fo	ollow-uj	p Perioc	l			Notes
Procedure/Visit Day (± 3 days for all	D 99	D 113	D 127	D 141	D 155	D 169	D 197 (± 7)	D 225	D 253 (± 7) EOS	ET	
visits unless otherwise noted)	W 14	W 16	W 18	W 20	W 22	W 24	W 28	W 32	W 36		
Safety Assessments											
Concomitant medication use	X	X	X	X	X	X	X	X	X	X	Concomitant medications are medications taken any time after the first dose of study medication until the last study visit.
Monitor for AEs	X	X	X	X	X	X	X	X	X	X	Nonserious AEs must be collected from the time of the first dose of the study treatment through the date of the follow-up or last visit. Monitoring for AEs will occur at every study visit.
Monitor for SAEs	X	X	X	X	X	X	X	X	X	X	All SAEs must be collected from the date of participant's written consent until 30 days after the final dose of the study treatment or participant's participation in the study if the last scheduled visit occurs at a later time. Monitoring for SAEs will occur at every study visit.
Physical and Metab	olic A	ssessm	ents								
Full physical examination									X	X	A full examination will include general appearance, skin, head, eyes, ears, nose, throat, neck, thyroid, chest/lungs, heart, abdomen, lymph nodes, extremities, height, and body weight.
Abbreviated physical assessment		X		X		X	X	X			Abbreviated examinations will include vital signs, weight, an abdominal exam, assessments of ascites and hepatic encephalopathy, and symptom-focused assessments.

Table 3 On-Treatment Procedural Outline IM025006: Part 1, Follow-up Period (Day 99 through Day 253)

				24-w	eek, Fo	ollow-uj	p Period	i			Notes

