2.2 Secondary Study Objectives

Part 1:

- To assess the effect of treatment with 90 mg QW BMS-986263 on the change in collagen proportionate area (CPA), as compared to placebo after 12 weeks of treatment
- To assess the effect of treatment with 90 mg QW BMS-986263 on the proportion of participants with ≥ 1 stage improvement in liver fibrosis (Ishak score), as compared to placebo after 12 weeks of treatment
- To assess the effect of treatment with 90 mg QW BMS-986263 on the proportion of participants with ≥ 2 stage improvement in liver fibrosis (METAVIR score), as compared to placebo after 12 weeks of treatment
- To assess the effect of treatment with 90 mg QW BMS-986263 on the proportion of participants with ≥ 2 stage improvement in liver fibrosis (Ishak score), as compared to placebo after 12 weeks of treatment

Statistical Analysis Plan Version Date: 19-Feb-2019

- To assess the effect of treatment with 90 mg QW BMS-986263 on the proportion of participants with a ≥ 15% reduction in liver stiffness as measured by magnetic resonance elastography (MRE) compared to placebo at Week 12
- To assess the effect of treatment with 90 mg QW BMS-986263 on the change in liver stiffness from baseline as measured by MRE compared to placebo at Week 12
- To assess the safety and tolerability of 45 mg QW and 90 mg QW BMS-986263 throughout 36 weeks of treatment and follow-up
- To assess the pharmacokinetics (PK) of 45 mg QW and 90 mg QW BMS-986263
- To describe the effect of treatment with 45 mg QW BMS-986263 on liver fibrosis after 12 weeks of treatment

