9.6.2 Adverse Events

All TEAE summaries will be generated based on the Safety Analysis Set by treatment group and total. A summary of TEAEs will be generated and will include the number of events reported and the number and percentage of participants reporting:

- at least one AE
- anv severe AE
- any treatment-related AE
- any severe treatment-related AE
- any AE with outcome of death
- any SAE
- any treatment-related SAE
- any AE leading to the discontinuation of study treatment
- any treatment-related AE leading to discontinuation of study treatment
- any AE leading to discontinuation from the study
- any treatment-related AE leading to discontinuation from the study.

A summary of AEs will be presented by MedDRA SOC and PT. A breakdown of the number and percentage of participants reporting each TEAE, categorized by SOC, PT, and maximum severity, will be presented. Note that counting will be by participant not event and participants are only counted once within each SOC or PT. An additional summary of treatment-related TEAEs by SOC, PT, and maximum severity will be presented.

Summaries of severe TEAE, treatment-related TEAE, severe treatment-related TEAE, TEAE with outcome of death, serious TEAE, treatment-related serious TEAE, TEAE leading to study treatment discontinuation. treatment-related TEAE leading to study treatment discontinuation, TEAE leading to study discontinuation, and treatment-related TEAE leading to study discontinuation will also be provided, grouped by SOC and PT.

Page 24 of 30

Statistical Analysis Plan Version Date: 19-Feb-2019

The first row on every treatment-emergent AEs summary will be the number and percentage of participants reporting at least one TEAE. Subsequent rows will be presented in descending order of participant counts in total with the most common SOC first, followed within each SOC by the PTs in descending participant count order.

A by-participant listing of all AEs will be provided. Details such as clinical signs and symptoms will be listed for infusion related reactions.

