9.6.4 Deaths and Serious Adverse Events

A summary of SAEs, categorized by SOC and PT and coded according to the MedDRA dictionary, will be presented by treatment group and total in the Safety Analysis Set. Note that counting will be by participant not event and participants are only counted once within each SOC or PT. All SAEs will be listed by participant. An additional summary of treatment-related SAEs will be presented by SOC and PT.

AEs with an outcome of death will be summarized by SOC and PT. All AEs with an outcome of death will be listed.

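### The 30-day TEAE window leaves nonserious AEs from about Day 109 to Day 253 of Part 1 without a clearly specified summary by arm, although the safety objective covers 36 weeks

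*SAP*

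**What the plan says.** - **Objective.** SAP 2.2 lists as a secondary objective: "To assess the safety and tolerability of 45 mg QW and 90 mg QW BMS-986263 throughout 36 weeks of treatment and follow-up".
- **Collection.** Protocol 1.2, Table 3 (Part 1 follow-up) states: "Nonserious AEs must be collected from the time of the first dose of the study treatment through the date of the follow-up or last visit". It marks AE monitoring at every follow-up visit up to Day 253. Protocol 8.6.2.1.1 gives the same period.
- **Window.** SAP 5.6 limits treatment emergence to events starting or worsening "after the first dose of study treatment and not more than 30 days after the last dose of study treatment". SAP 5.8 counts only BMS-986263 or placebo as study treatment, so premedication does not extend the window.
- **AE tables.** SAP 9.6.2 specifies grouping by treatment for TEAE summaries. The overview, severity, relatedness and discontinuation tables are all of this kind. One sentence differs: "A summary of AEs will be presented by MedDRA SOC and PT". It names neither a period nor a grouping. The section ends with: "A by-participant listing of all AEs will be provided".
- **SAEs and deaths.** SAP 9.6.4 states: "A summary of SAEs, categorized by SOC and PT and coded according to the MedDRA dictionary, will be presented by treatment group and total". Related SAEs and fatal AEs are also tabulated there. No TEAE limit is given.
- **Protocol analysis text.** Protocol 9.3.2 provides for treatment-emergent AEs during the study to be summarised by treatment. It does not define treatment-emergent and gives no 30-day limit.

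**The concern.** The objective and the data collection run to Week 36, but the tables run to 30 days after the last dose. Followed as written, the visible SAP has no clearly specified arm-level summary of nonserious AEs for most of the Part 1 follow-up. A late imbalance between arms would have to be found by reading listings and rebuilding denominators by hand under 1:2:1 allocation. An AE that leads a participant to leave the study on Day 200 would fall outside the study-discontinuation table. The tables of AEs leading to stopping study treatment lose essentially nothing, because such events occur while dosing is under way.

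The window also follows each participant's own last dose, and Protocol 8.4.6.1 keeps those who stop dosing under follow-up. If early stopping differs by arm, the TEAE percentages compare observation periods of unequal length.

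A related inconsistency affects the late SAE tables. After 30 days, Protocol 8.6.2.1.1 asks for reports only of SAEs judged related to study drug or a study procedure. The Schedule of Activities instead extends SAE collection through the participant's "participation in the study if the last scheduled visit occurs at a later time". How complete the late SAE counts are depends on which rule the sites followed.

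**Working it through.** No sample-size or error-rate figure is involved; this is day arithmetic.

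**1. Last Part 1 dose.** Three sources agree.
- The Table 2 note for the Day 85 PK sample says "Collect sample 1 week after last administration", and Protocol Table 12 gives 168 h: 85 − 168/24 = Day 78.
- Table 12 gives 504 h for the Day 99 sample: 99 − 504/24 = Day 78.
- Twelve weekly doses from Day 1: 1 + 7 × 11 = Day 78.

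The SAP 5.9 duration formula is consistent with this: (78 − 1 + 7)/7 = 12 weeks.

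**2. Window end.** 78 + 30 = Day 108. The ±3-day visit window on the last dose makes this Day 105 to Day 111. The documents do not state Day 108; it follows from SAP 5.6.

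**3. Time outside the window.** Week 36 is 36 × 7 + 1 = Day 253.
- Days 109-253: 253 − 108 = 145 days.
- Share of all study days: 145/253 = 57%.
- Share of follow-up after Day 85: 145/(253 − 85) = 145/168 = 86%.
- With the ±7-day window on the final visit, and the last dose held at Day 78, the gap is 138 to 152 days.

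**4. Visits.** Table 3 schedules follow-up AE monitoring on Days 99, 113, 127, 141, 155, 169, 197, 225 and 253. Only Day 99 is on or before Day 108, so 8 of 9 visits fall after the window.

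**5. Early stopper (illustration).** If the last dose is on Day 29 and follow-up continues to Day 253, the window closes on Day 29 + 30 = Day 59. That leaves 253 − 59 = 194 days outside (194/253 = 77%).

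**6. Possible share of events (assumption).** The documents give no AE rates. Let r be the daily AE rate after Day 108 divided by the rate before it. The share of AEs starting outside the window is then 145r/(108 + 145r).

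| r (assumed) | Calculation | Share outside |
|---|---|---|
| 0.10 | 14.5/122.5 | 12% |
| 0.25 | 36.25/144.25 | 25% |
| 0.50 | 72.5/180.5 | 40% |

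This share counts all AEs, including SAEs that SAP 9.6.4 tabulates separately.

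**The case against.** **The protocol promises only treatment-emergent AEs, and the SAP is free to define them.** That is correct, and SAP 5.6 does not contradict Protocol 9.3.2. The mismatch is with the 36-week objective and the collection period.

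**Thirty days is generous.** Inclusion criterion 6e puts five half-lives at 5 days, so the window is six times that, and later events are off-drug. This supports keeping the TEAE tables as they are. It does not answer an objective that explicitly includes follow-up.

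**Follow-up safety is analysed in other ways.** SAEs and deaths are tabulated in SAP 9.6.4. Raised ALT, AST, bilirubin and AFP are counted at any post-baseline time. Labs, vital signs and ECGs are summarised by visit. All of this stands, and it confines the gap to nonserious AEs. With arms of roughly 15, 30 and 15 and no formal testing, reading a listing is feasible, but it is not a specified comparison.

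**The sentence on a summary of AEs by SOC and PT may mean all AEs.** It may, and that would remove much of the gap. It sits among TEAE tables, however, and gives no period or grouping. SAP 5.7, SAP 9.6.3 and the TFL shells are not available in the public text, and nothing is claimed about them; they may contain a table that covers this period.

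**Protocol 8.6.2.1.1 governs reporting of SAEs, not collection.** That reading is possible. The two passages still need to be reconciled before late SAE counts can be interpreted.

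**The figures are days, not events.** This is true. The event shares in the working rest entirely on assumed rate ratios.

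**Conclusion.** The concern holds and should be fixed. Applied exactly, the 30-day rule leaves late nonserious AEs assured only in a listing, for 145 of 253 days and 8 of 9 follow-up visits in a participant who completes dosing. This rests on a last dose on Day 78, follow-up to Day 253, and reading the by-arm tables in SAP 9.6.2 as limited to TEAEs. Confidence is medium, because one sentence in that section is ambiguous and parts of the SAP and the table shells cannot be seen. The effect on any safety conclusion cannot be sized from the documents.

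**What to change.** 1. Keep the 30-day TEAE tables.
2. In SAP 9.6.2, add overview and SOC/PT tables by treatment group for (a) AEs from first dose to the last visit (Day 253) and (b) AEs with onset more than 30 days after the last dose.
3. State whether the SOC/PT summary of AEs in SAP 9.6.2 and the SAE and death tables in SAP 9.6.4 are limited to TEAEs.
4. Reconcile the SAE period in Protocol 8.6.2.1.1 with the Schedule of Activities, and footnote the SAE tables with the period that applies.

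The cost is SAP wording, the protocol reconciliation and a few extra tables from data already collected. The downside is longer output, with off-treatment events shown beside on-treatment ones.

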5.8 Study Treatment

For the purposes of the calculations included in this SAP, study treatment will include only doses of BMS-986263 or placebo.

5.9 Treatment Duration (weeks)

Treatment duration (weeks) will be calculated as:

Part 1: (date of last dose of study treatment* during Part 1 – date of first dose of study treatment during Part 1 + 7)/7. The additional 7 days are added to account for the last week of treatment.

*for the purposes of these calculations, study treatment refers to BMS-986263 or placebo.

5.10 Study Day

Study day is defined relative to the date of the first dose of study treatment. For assessments that occur on or after this visit date, study day is calculated as (assessment date – first dose date + 1). For assessments that occur prior to first dose date, study day will be calculated as (assessment date – first dose date); there is no Study Day 0. Study Day 1 is the day of first study treatment received.

5.11 Prior and Concomitant Medications

All medications taken from within 4 weeks before the first dose of study treatment until last visit must be recorded on the eCRF. Prior medications are defined as medications taken within 4 weeks of the first dose of study treatment and discontinued before the first dose of study treatment. Concomitant medications are defined as any medication taken after the first dose of study treatment until last visit

Imputation Rules for Partial Dates (D = day, M = month, Y = year)				
Parameter	Missing	Additional Conditions	Imputation	
Start date	D only	M and Y same as M and Y of first dose	Date of first dose of study	
		of study treatment	treatment	

Page 16 of 30

Sponsor: Bristol-Myers Squibb Statistical Analysis Plan
Protocol no: IM025006 Version Date: 19-Feb-2019

Parameter	Missing	Additional Conditions	Imputation
		M and/or Y not same as date of first dose of study treatment	First day of month
	M and D	Y same as Y of first dose of study treatment	Date of first dose of study treatment
		Y not same as Y of first dose of study treatment	Use Jan 01 of Y
	M, D, and Y	None – date completely missing	Day prior to date of first dose of study treatment
Stop date D only	M and Y same as M and Y of the Follow-up visit	Date of the Follow-up visit	
		M and/or Y not same as date of the Follow-up visit	Last day of month
	M and D	Y same as Y of the Follow-up visit	Date of the Follow-up visit
		Y not same as Y of the Follow-up visit	Use Dec 31 of Y
	M, D, and Y	None – date completely missing and NOT ongoing	Date of the Follow-up visit

Note: In all cases, if an estimated start date is after a complete stop date, use the first day of the stop date month. Similarly, if the estimated stop date is before a complete or imputed start date, use the last day of the start day month.

For example for a concomitant medication start date imputation, if a participant is dosed on 15MAY2018 and has a concomitant medication start date reported as MAY2018 the imputation would be 15MAY2018, but if the concomitant medication start date was reported as JUN2018 the imputation would be 01JUN2018.

For example for a concomitant medication stop date imputation, if a participant follow-up visit or cutoff date is 15MAY2018 and has a concomitant medication stop date reported as MAY2018 the imputation would be 15MAY2018, but if the concomitant medication stop date was reported as MAR2018 the imputation would be 31MAR2018.

Note, if a medication is missing an end date and is recorded as ongoing, it will be classified as concomitant. Partial dates should be imputed before the classification of prior or concomitant.

Statistical Analysis Plan Version Date: 19-Feb-2019

5.14 Other Calculations

Method of BMI Calculation:

- Use actual height and weight collected on the same day. Whenever possible, body weight should be measured using the same scale throughout the study.
- To calculate BMI:
 - Convert weight pounds to kg (kg = pounds / 2.2)
 - Convert height inches to centimeters (cm = inches × 2.54)
 - BMI = (weight in kg) / (height in cm/100) 2
 - o Round to 1 decimal place (if 0.05 or greater, round up)

6.0 Analysis Sets

The following analysis sets are defined for analysis purposes:

Analysis Set	Description
Enrolled ^a	All participants who sign informed consent
Randomized	All participants who are randomized to a treatment, analyzed as per randomized treatment.
Modified intent-to-treat (mITT)	All participants who are randomized to a treatment and receive at least 1 dose of study treatment analyzed as per randomized treatment. All primary efficacy analyses will be conducted using this analysis set.

Page 18 of 30

Spangar: Printal Myora Squibb

Sponsor: Bristol-Myers Squibb Statistical Analysis Plan
Protocol no: IM025006 Version Date: 19-Feb-2019

Pharmacokinetic	All participants who receive at least 1 dose of BMS-986263 and have any available concentration-time data
Safety (As-treated)	All randomized participants who receive at least 1 dose of study treatment, analyzed according to the treatment actually received. The treatment may differ from that to which the participant was originally randomized. All safety analyses will be conducted using this analysis set.

^a For the Enrolled Analysis Set, there may be some cases where data is analyzed by treatment group. If this is the case, any participants who are in the Enrolled Analysis Set but were not randomized (i.e. not in the Randomized Analysis Set), those participants will not be included in any particular treatment group, but will be included in any overall summary.

